2.1.2 Potential risk from combination antibiotic therapy and mitigation of this risk

This risk is related to the potential for drug interactions and adverse drug reactions, potential for increased risk of antibiotic resistance, and potential for increased risk of *C.difficile* infection. These risks are addressed as described above by avoiding drugs known to interact with clarithromycin, by excluding patients with specific risk factors for serious adverse effects and by reminding sites to follow their usual antibiotic policy.

2.1.3 Inclusion of women of childbearing potential and contraception requirements

The SmPC for clarithromycin advises against use in pregnancy without careful assessment of risks versus benefits as there is the potential for fetal harm but contraception use is not mandated. All women of childbearing potential will require a negative pregnancy test (urine or blood) before they can participate in the CLASP study.

It is anticipated that due to the severity of their condition, the vast majority of CLASP participants will remain inpatients for the duration of clarithromycin treatment. For women of childbearing potential, it may be clinically inappropriate to continue pre-stroke contraception methods such as combined oral contraception due to pro-thrombotic risks. It is also not practical to mandate the use of other contraception methods given the limited duration of systemic clarithromycin exposure and clinical context. The extent of stroke-induced injury may also mean that discussions around contraception methods could cause significant distress for some participants and may not be appropriate given the clinical condition of the participant. The extent to which contraception measures need to be discussed

at the point of enrolment will therefore be at the discretion of the Principal Investigator (or designee). Should the clinical condition of the participant be such that appropriate contraception advice is likely to be required prior to the end of the clarithromycin exposure period, the local site team must ensure appropriate advice is provided. This must be fully documented in the participant's medical records.

Where necessary, women of childbearing potential will be required to:

- Use highly effective methods of contraception, OR
- Other birth control methods with a failure rate of less than 1% OR
- Agree to abstain from sexual intercourse with a male partner (unless confirmed vasectomy) until at least 3 days (72 hours) after the last dose of clarithromycin.

Should a pregnancy occur, it will be reported in an expedited fashion in accordance with Adverse Event reporting requirements in the UK. Acceptable birth control methods are outlined in Appendix 1. This approach is felt to be pragmatic and justified given the severity of the clinical condition and limited period of exposure to clarithromycin.

2.1.4 Changes to antibiotic therapy during the treatment phase of the study

Clarithromycin is used in approximately 10% of people with PSP, although it will be used in people who are penicillin allergic and is routinely used for severe community acquired pneumonia in the hospital setting.

It is possible that participants will deteriorate, leading to clinical teams expanding antibiotic coverage, or develop other indications for antibiotic therapy. These decisions will be taken by clinical teams and, provided any additional drugs used do not have a known severe interaction with clarithromycin or appear on the list in the list of prohibited medicines in Appendix 2, treatment with clarithromycin can continue.

2.1.5 Potential risk of unblinding of outcome assessors

The participant follow-up at 90 days will be carried out by blinded central assessors who are not part of the clinical research team. There remains a risk of unblinding to treatment by the participant or caregiver during follow-up interviews. Central assessors will remind participants and caregivers that they should not mention any medication given to the participant unless directly questioned about medications at the time of interview.

With the above mitigations, the trial is categorised as:

• Type A = Risk no higher than the risk of standard medical care

3 OBJECTIVES AND OUTCOME MEASURES/ENDPOINTS

3.1 **Primary objective**

The primary objective of the trial is to determine whether 5 days of treatment with clarithromycin in addition to usual non-macrolide antibiotic treatment for PSP improves functional outcome at 90 days after stroke in comparison to usual non-macrolide antibiotic treatment.

3.2 Secondary objectives

This trial also seeks to determine whether 5 days of treatment with clarithromycin in addition to usual non-macrolide antibiotic treatment for PSP:

- Reduces mortality at 90 days
- Increases home time by 90 days

- Reduces cardiovascular mortality at 90 days
- Reduces urgent or unplanned readmissions at 90 days
- Reduces recurrent stroke at 90 days
- Reduces major cardiovascular events at 90 days
- Improves quality of life at 90 days
- Improves stroke-related health status at 90 days
- Reduces caregiver burden at 90 days
- Is safe
- Is cost-effective from the perspective of NHS England

3.3 Outcome measures/endpoints

Outcome measures were determined after discussions with PPIE collaborators and a search of the COMET Initiative database (terms "Neurology", "Acute Stroke", "Published") for acute stroke trial core outcome sets. Two published recommendations were identified [29, 30] which incorporate survival, stroke recurrence, patient reported outcome measures (PROMs) across all domains including motor/non-motor problems, cognition, mood. However, whilst mRS is a standard outcome measure, there is no ubiquitous or agreed set of outcome/assessment scales used consistently in acute stroke trials. Outcome measures were chosen in partnership with the CLASP PPIE group and are aligned with the above recommendations to include survival, stroke recurrence and PROMs (quality of life and stroke-related health status). Caregiver burden was considered to be an important outcome measure by the PPIE group in view of the relatively poor prognosis of patients with PSP. The primary and secondary outcome measure scales (mRS [31], EQ-5D-5L [32], Home time [33], Stroke Impact Scale [34] and Zarit Caregiver Burden [35]) are well-established in stroke research and can be collected using telephone and postal assessments. The assessments will be centralised and undertaken by research staff blinded to treatment allocation. The timing of outcome assessments (described below) refers to time from randomisation.

3.3.1 Primary outcome

Modified Rankin Scale (mRS) score (a measure of functional outcome) at 90 days (+/-14 days) assessed by virtual online assessment or telephone using centralised, blinded, trained raters.

Postal questionnaires can be used only in the event that online or telephone assessment is not possible to avoid loss to follow-up.

3.3.2 Secondary outcomes

- All-cause mortality at 90 days
- Days spent in pre-admission usual place of residence at 90 days
- Cardiovascular mortality at 90 days
- Non-elective admissions by 90 days
- Stroke at 90 days
- Major cardiovascular events at 90 days
- EQ-5D-5L at 90 days
- Stroke Impact Scale at 90 days
- Zarit Caregiver Burden (ZBI-12) interview
- Clostridioides difficile infection within 90 days
- Ventricular arrhythmia within 7 days
- Health and social care resource use (index hospitalisation and post-discharge health and social care contact) up to 90 days to inform health economic analysis.

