7.6 Follow-up assessments

The trial will comprise of 4 visits: Screening, Randomisation, Day 7 and Day 90 follow-up.

The Day 7 (+3) visit will be carried out by research staff who will collect information such as the following from case notes:

- Information on safety outcomes including *C.difficile* infection, and occurrence of defined SAEs (see section 9)
- Clarithromycin dose, doses administered and route(s) of administration (including reasons for any non-administered doses)
- Other antibiotics and doses received
- Highest CRP concentration (mg/L) to Day 7 (+3) visit
- Highest WBC count and neutrophil count (x10⁹/l) to Day 7 (+3) visit
- Highest RR (/minute) to Day 7 (+3) visit
- Highest temperature (°C) recorded to Day 7 (+3) visit
- Highest NEWS-2 score to Day 7 (+3) visit
- Lowest oxygen saturations (%) to Day 7 (+3) visit
- Oxygen requirements
- Presence of unilateral or bilateral chest signs on examination
- Findings from clinical CXR or other chest radiology
- Contact details for follow-up (participant, consented caregiver, GP)

Participants and their caregivers/GP can be contacted by telephone, email or post between 1 week and 1 month prior to the due date of the Day 90 visit to confirm contact details and ongoing participation.

The Day 90 visit will involve local data collection by the research team and a centralised assessment (+/-7 for local research staff follow-up, +/-14 for central follow-up) by video or telephone.

Local research staff will collect the following data from the medical record at Day 90 (+/-7):

- Length of hospital stay (days)
- Mortality
- Discharge destination (remains in hospital, home, care home)
- Urgent or unplanned re-admissions
- Recurrent stroke or other vascular events

The centralised assessment will then be undertaken by appropriately trained University of Manchester staff blinded to treatment allocation. This will take place via video or telephone assessment after local research staff have carried out the mortality check. They will collect information such as the following measures:

- mRS
- Quality of Life (EQ-5D-5L)
- Stroke Impact Scale (SIS)
- Home time (number of days at usual place of residence [immediately prior to their admission] at day 90)
- Health and social care resource use (index hospitalisation and post-discharge health and social care contact up to 90 days)
- Caregiver quality of life (EQ-5D-5L)
- Zarit Caregiver Burden (ZBI-12)

The Day 90 visit marks the end of the study.

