9.2 Operational definitions for (S)AEs

Clarithromycin has been in clinical use for more than 30 years and is widely used for the treatment of respiratory tract infections, including community acquired infection. The IMP is generally well tolerated with the most common side effects being mild gastrointestinal adverse reactions. It has a well-defined safety profile obtained throughout the lifetime of the drug and therefore it is highly unlikely that this trial will identify any novel (serious) adverse reactions. Participants are anticipated to exhibit complications related to the index stroke, associated complications, and comorbidities resulting in prolongation of hospitalisation and high numbers of adverse events due to the short time frame between the index stroke and the commencement of treatment with IMP. In addition, participants may receive multiple treatments to manage stroke symptoms, and associated underlying medical conditions. Under these circumstances, participants may be subject to multiple ongoing adverse events and serious adverse events and it may be difficult for investigators to distinguish AEs and SAEs that are a consequence of disease processes and concomitant medications from those that have a causative relationship with the IMP(s) due to a high level of confounders. Taking the above into account, (S)AEs (except for those detailed below) will not be reported via the eCRF but must be recorded within participant medical records in accordance with GCP.

The principal risk associated in adding clarithromycin to the usual care pathway is the potential for prolongation of the QT and QTc interval resulting in cardiac arrythmias; primarily ventricular arrythmias. In addition, treatment with antimicrobial therapies, including macrolides, can be associated with an increased risk of developing infection with *C.difficule*. While cardiac arrythmias and *C.diff* infections may not necessarily always meet the regulatory definition of serious, they will almost certainly require intervention to prevent them from become so and are significant medical events.

Therefore, the following events will be subject to expedited reporting as serious adverse events from the point of randomisation until day 3 post cessation of trial IMP (generally, day 7 or earlier but could be up to day 10 after randomisation):

- Any suspected or confirmed infection with *C.difficile* irrespective of whether the event meets the regulatory definition of serious.

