- Any incidence of sustained (>30s) ventricular arrythmias irrespective of whether the event meets the regulatory definition of serious.
- Any serious adverse event suspected to be directly related to the IMP that is considered unexpected by the local investigator.

Note: If an event occurs more than 72 hours after cessation of IMP that is considered related to IMP, it must be reported.

Hospitalisation, or prolongation of hospitalisation, related to the index stroke and associated complications, or other underlying medical conditions are excluded from reporting as a serious adverse event for the purpose of this trial. Such events should be recorded within the eCRF at visit 2 and visit 3 (day 90) as per routine data collection and will be used to inform trial endpoints. The IDMC will review event rates on a regular basis to ensure the frequency of these events is line with expectations.

The following are exempted from recording within the eCRF and reporting as SAEs:

- Routine treatment or monitoring of the studied indication not associated with any deterioration in condition.
- Treatment that is elective or pre-planned, for a pre-existing condition not associated with any deterioration in condition, e.g. pre-planned hip replacement operation which does not lead to further complications.
- Any admission to hospital or other institution for general care where there was no deterioration in condition.
- Treatment on an emergency, outpatient basis for an event not fulfilling any of the definitions of serious as given above and not resulting in hospital admission.

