9.4 Recording and Reporting of Serious Adverse Events (SAEs)

9.4.1 Initial reports

All SAEs as defined within section 9.2 must be recorded within the study eCRF from the point of informed consent until day 3 post cessation of trial IMP (generally, day 7 or earlier but could be up to day 10 after randomisation).

Protocol defined SAEs must be reported within the eCRF within 24 hours of investigator or study team awareness of the event.

Full details of these SAEs will be recorded in the eCRF. The following information will be collected at a minimum:

- Nature of the event
- Event duration (start and end dates, if applicable)
- Relationship to trial medication in the opinion of the investigator
- If related, whether the reaction would be considered expected or unexpected
- Action taken
- Outcome (if applicable)
- Seriousness criteria

All protocol defined SAEs will be subject to review by the local Principal Investigator, or their medically qualified designee(s), within 7 days of the site becoming aware of the event for fatal or life-threatening SAEs and within 15 days for all other SAEs.

Any change of condition or other follow-up information should be added to the eCRF as soon as it is Serious Adverse Events must be followed up until the event has resolved or a final outcome has been reached.

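### C. difficile infection is a 90-day safety outcome, but the protocol defines its collection in both arms only to about day 10

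*Protocol*

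**What the plan says.** Protocol section 3.3.2 lists "Clostridioides difficile infection within 90 days" among the secondary outcomes. The trial summary gives it and ventricular arrhythmia within 7 days as the two measures behind the safety objective. Section 3.3 fixes the clock: "The timing of outcome assessments (described below) refers to time from randomisation".

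Section 7.6 then sets out what is collected and when.

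- At Day 7 (+3), research staff take from the case notes "Information on safety outcomes including *C.difficile* infection, and occurrence of defined SAEs (see section 9").
- At Day 90 the local review is introduced by "Local research staff will collect the following data from the medical record at Day 90 (+/-7"). Five items follow: time in hospital, death, where the participant was discharged to, emergency re-admission, and further stroke or vascular events. C. difficile is not among them.
- The central Day 90 interview list covers function, quality of life, stroke impact, home time, resource use and caregiver measures. It does not mention C. difficile either.

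Section 9.2 makes any suspected or confirmed C. difficile infection a protocol-defined SAE, reportable "from the point of randomisation until day 3 post cessation of trial IMP". Section 9.4.1 gives the matching rule for data entry: "All SAEs as defined within section 9.2 must be recorded within the study eCRF from the point of informed consent until day 3 post cessation". Section 9.2 keeps all other adverse events in the medical notes and out of the electronic case report form (eCRF). It adds one exception for later events: "If an event occurs more than 72 hours after cessation of IMP that is considered related to IMP, it must be reported".

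The schedule in Appendix 9 ticks the SAE safety row at both Day 7 (+3) and the Day 90 local follow-up.

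**The concern.** The outcome is defined over 90 days from randomisation in both arms, but the collection instructions stop within the first ten or so. Section 2.1.1 itself says that any excess C. difficile risk from clarithromycin is uncertain, so the comparison is one that the trial is expected to inform.

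Two things are at stake. Cases arising after the early window, in hospital or after discharge, may never be entered for either arm, so the reported 90-day figure would be too low. In addition, the only explicit rule that brings a later case in depends on attribution to the trial drug. The usual-care arm receives no trial drug (section 7.3), so no case there can meet the rule, and the date from which its reporting window runs does not exist. In the clarithromycin arm the attribution is made by investigators who know the allocation (section 7.4).

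**Working it through.** **1. Length of the reporting window.** The inputs are ten doses at 12-hour intervals, that is 5 days, stretched to at most 7 days if doses are missed (section 8.6), and a window closing 3 days after the last dose (section 9.2).

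- Uninterrupted dosing: 5 + 3 = about day 8.
- Longest permitted dosing: 7 + 3 = day 10.

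The second result reproduces the protocol's own figure: "until day 3 post cessation of trial IMP (generally, day 7 or earlier but could be up to day 10 after randomisation"). The Day 7 (+3) visit also ends by 7 + 3 = day 10, so both sources stop there at the latest.

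**2. Share of the horizon without defined collection.** 90 − 10 = 80 days, and 80/90 = 89%. At best, 10/90 = 11% of the horizon is covered.

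**3. Routes by which a case after day 10 could enter the data.**

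- Day 90 local review (7.6): five listed items, none of them C. difficile.
- Central interview (7.6): C. difficile is not named. The assessors of the primary outcome have no access to patient records (7.4), so they could not verify a report.
- Re-admissions at Day 90 (7.6): an admission caused by C. difficile would count as a re-admission, not as a C. difficile outcome. Cases in the index stay or in the community would not appear.
- Stroke-related or comorbidity-related hospitalisations recorded at visit 3 (9.2): this applies to both arms without a relatedness test, but it creates no C. difficile item.
- SAE row at Day 90 (Appendix 9): SAEs for this trial are those of section 9.2, which carry the closed window. The two places conflict.
- Late event judged related to the trial drug (9.2): explicit, but open only to the clarithromycin arm.

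**4. Effect on the comparison.** Suppose the true 90-day risk p is the same in both arms. Let f be the share of events falling inside the early window and a the share of late clarithromycin-arm events judged related, reported and counted in the outcome.

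- Recorded risk, usual care: p × f.
- Recorded risk, clarithromycin: p × [f + (1 − f) × a].
- Recorded risk ratio: [f + (1 − f) × a] / f. The risk p cancels.

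If a = 0 the ratio is 1, so it is undistorted, but a share 1 − f of events is lost in each arm. If a > 0 the ratio exceeds 1 although the true risks are equal. The protocol gives neither f nor a. Taking f from 0.2 to 0.6 and a from 0 to 1, purely as assumptions, the ratio runs from 1.0 to (0.2 + 0.8)/0.2 = 5.0. A range that wide shows the direction of the bias and nothing about its likely size.

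**The case against.** The strongest reply is that the rule on late related events belongs to pharmacovigilance and does not define the outcome. No passage says that the 90-day outcome will be built from SAE reports, and section 10.3.3 names no method for C. difficile. This stands. A reader might infer that the comparison is biased by design, but that needs late attributed reports to be counted in the outcome, which the protocol does not state. If they are not counted, the defect is under-ascertainment in both arms.

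A second reply is that Day 90 capture is intended. Appendix 9 ticks safety at Day 90, section 9.2 provides for hospitalisation records at visit 3, the central list is worded as open-ended, and section 11.2 promises an eCRF holding everything that the protocol needs. These do show intent, and the eCRF may already hold a suitable field. None of them, however, tells a site to look for C. difficile at Day 90 in every participant, and the Day 90 local list is worded as complete. The Appendix 9 tick conflicts with the section 9 window and does not repair it.

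Two further inferences are tempting, and the documents do not support them.

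- **Ventricular arrhythmia within 7 days.** It might seem to suffer the same fault, because SAE reporting is tied to stopping clarithromycin. But the Day 7 (+3) visit is timed from randomisation, applies to both arms, cannot fall before day 7 and collects safety outcomes. The arrhythmia outcome is covered.
- **The ±7-day local window.** It might seem to cut 90-day events short, because a review may be done on day 83. The window is the same in both arms, a loss of 7 days is only its ceiling, all deaths must be entered in the eCRF (section 9.10), and resource use to 90 days is a second source for re-admissions.

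**Conclusion.** The point holds as a gap between a stated outcome and its collection. At least 80 of the 90 days (89%) have no defined collection of C. difficile that treats the arms alike. That figure rests only on the protocol's dosing limit and reporting window.

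The consequence is certain in kind: followed as written, the plan misses later cases in both arms. Bias against clarithromycin is conditional on counting late attributed reports. Neither the number of cases missed nor the size of any bias can be derived from the documents, because they give no C. difficile rate, timing or attribution share.

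This should be fixed. It concerns one secondary safety outcome and leaves the primary analysis, the sample size and the interim rules untouched. An analysis plan cannot repair it later, because events that were never entered cannot be analysed.

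**What to change.** 1. In section 7.6, add C. difficile infection (yes/no, date, toxin result) to the Day 90 local record review for every participant in both arms, regardless of attribution and timed from randomisation.
2. State that the 90-day outcome is derived from this item together with the Day 7 (+3) data, and not from SAE reports.
3. In sections 9.2 to 9.4, define from randomisation when the SAE window ends for usual-care participants. While doing so, reconcile its start, which is randomisation in 9.2 and consent in 9.3 and 9.4.1.
4. Keep the relatedness condition for expedited reporting only.
5. Reconcile the Day 90 safety tick in Appendix 9 with the section 9 window.

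The cost is one eCRF item on a review that sites already carry out, a little more data entry, and an amendment to the wording. Participants already past Day 90 when the change takes effect would need a retrospective look at their notes, so an early amendment is cheaper. If the sponsor does not want the extra item, the alternative is to shorten the stated outcome to the period actually collected, measured from randomisation in both arms. That would give up the information on later infections.
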